Consistent use of antiretroviral medications by adults living with HIV can suppress plasma HIV-1 RNA (viral load) to undetectable levels and thereby improve survival rates and quality of life, and reduce HIV-related infections, health care costs, and transmission of HIV. Despite the potential benefits of antiretroviral therapy, adults living with HIV have not been reliably engaged in HIV care or sustained on antiretroviral medications. Few interventions have been shown effective in increasing adherence and suppressing viral loads to undetectable levels, and no treatments have produced long-term effects that sustain after the intervention is discontinued. Interventions that provide incentives to patients when they meet required therapeutic goals have been demonstrated extraordinarily effective in promoting therapeutic behavior change in diverse populations and they have shown promise in promoting adherence to antiretroviral medications and suppression of viral loads. However, only limited evaluations of these interventions have been conducted to promote adherence to antiretroviral medications and suppress viral loads, those evaluations have not employed optimal parameters of incentive interventions, and they have not produced levels of viral load suppression that are needed clinically. We propose to evaluate a novel incentive intervention to promote suppression of viral load in people living with HIV that will employ empirically-based parameters that have been proven critical to the effectiveness of incentive interventions. Participants (N = 200) from two medical clinics that serve adults living with HIV in Baltimore will be randomly assigned to an Incentive or a Usual Care Control group. Incentive group participants will receive incentives for maintaining suppressed and undetectable viral loads. The incentive program will employ high magnitude incentives, provide incentives for decreases in viral load early in treatment before a patient's viral load has reached undetectable levels, arrange frequent incentives early in treatment and reduce the frequency of incentives as participants achieve progressively longer periods of viral load suppression, arrange a schedule of escalating incentives for sustained suppression of viral load, and the intervention will be maintained for two years. Usual Care Control participants will only receive the standard HIV medical care offered in their clinic. Assessments will be conducted every 3 months throughout the two years of treatment and every 6 months throughout the year following treatment. The primary outcome measure will be the percentage of participants that have undetectable viral loads at the 3-month assessments conducted throughout the 2-year intervention period. Secondary measures will include adherence to HIV care and post-treatment outcomes. We will also assess moderators and mediators of the effects of the incentives on the suppression of viral load, and conduct cost-effectiveness and cost-benefit analyses. If the incentive intervention maintains suppressed viral load and is economically sound, it could be used to improve the health of adults living with HIV, reduce health care costs, and reduce HIV transmission in the community.

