During the research interviews, participants will be asked to complete a contact information sheet. The contact information sheet will include the participant's contact information as well as the contact information of family members or other individuals we may contact by phone or in writing in order to locate the participant for future research interviews. Participants who do not qualify for the study will be referred to services that they need or want. We have used similar recruitment procedures in prior studies (e.g.,

Donlin et al., 2008; [name] et al., 2007). See the Letters of Support section for letters from the Medical Directors of these clinics.

Standard HIV Medical Care

Upon enrollment, participants will be taught about the benefits of HIV medical care, ART adherence and the need to maintain nearly perfect adherence. Participants will be able to earn incentives for engaging in this education. Participants will be able to earn up to about \$100 for completing the program. Some or all of the training may be given through a computer-based training program. We may also evaluate the effectiveness of the education program by giving participants tests before and after participants complete parts or all of the training program. We may re-administer the test at the end of the intervention to measure retention.

If a participant is not currently receiving HIV medical care, the participant will be referred to an HIV medical care clinic. Participants will typically receive their HIV medical care at the Comprehensive Care Practice or the Chase Brexton Health Services clinic.

Experimental Design

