Participants (N = 200) who complete the HIV Medical Care Education program will be randomly assigned to a Usual Care Control group or the Incentive group. A computerized urn randomization procedure (Wei & Lachin, 1988) will be used to balance groups on five baseline characteristics that may influence outcome: (1) opiate or cocaine positive urine sample at intake to the study (Y/N); (2) Self-reported use alcohol to intoxication on 20 or more days in the past 30 on the ASI (Y/N); (3) health literacy as assessed on the TOFHLA (score \leq the rolling median, Y/N); (4) impulsivity as assessed by delay discounting (k value from the raw discounting data for each participant, which is an index of impulsivity (\leq the rolling median of k, Y/N); and (5) depression as assessed by the Beck Depression Inventory (score \leq the rolling median, Y/N). Participants will be stratified by DSM V cocaine, opiate and alcohol dependence, health literacy, and depression at intake because drug use (Mimiaga et al., 2013), health literacy (Kalichman et al., 2008), and depression (Murphy et al. 2013) has each been associated with poor ART adherence. Participants will be stratified based on measures of impulsivity because high levels of impulsivity have been associated with poor health decision making and adverse health behaviors (Axon et al. 2009; Bickel et al. 2014; Bradford et al., 2010). Participants will be taught the details of their group with written instructions and quizzes. Participants will earn up to about \$15 for answering questions on the quiz.

Incentive Group

The Incentive group will receive the novel empirically-based incentive intervention to promote long term suppression of HIV-1 RNA (viral load) being evaluated in this study. The incentive intervention will employ features and parameters that have been shown critically important to promote therapeutic behavior change in drug users and other populations (Higgins et al., 2008; Lussier et al., 2006; [name] et al., 2011). Participants will be taught the details of the incentive program with written instructions and quizzes.

A Prescription for ART. When a participant gets assigned to the Incentive group, he/she will be asked if he/she has a current prescription for ART and if he/she has at least a 2-day supply of medication. As described below, blood draws and the incentive program described below will not begin until the participant has an active ART prescription and has at least a 2-day supply of medication.

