Specific Aim. Assess the cost-effectiveness of the empirically-based incentive intervention for undetectable viral loads. We will assess incremental cost-effectiveness ratio (ICER) by dividing the difference in costs of two interventions by the difference in effects of the two interventions during the 2-year intervention evaluation period on viral load suppression (see below). The ICER can be interpreted as dollars spent per unit of desired outcomes gained. The Incentive Intervention should yield a better ICER.

Specific Aim. Assess the cost-benefit of empirically-based incentive intervention for undetectable viral loads. We will perform a Cost-Benefit Analysis (CBA) to examine the monetized benefits relative to costs for the Usual Care Control and Incentive intervention conditions. The economic outcomes are health care utilization during the 2-year intervention evaluation period (see below). We expect that the Incentive Intervention will yield greater economic benefits relative to its costs than the Usual Care Control.

Measures assessed repeatedly over time will be analyzed with a longitudinal logistic regression model. Within-person correlated outcomes will be handled using generalized estimating equations (GEE; Zeger, Liang, & Albert, 1988). Measures assessed once will be analyzed using logistic regression. The magnitude of effects will be expressed using odds ratios with 95% CI. Intent-to-treat analyses will be adjusted for covariates used for stratification (Pocock et al., 2002). Two-sided tests with p-values <.05 will be considered significant.

- b. Statistical plan including sample size justification and interim data analysis.

STATISTICAL ANALYSES

Measures assessed repeatedly over time will be analyzed with a longitudinal logistic regression model. Within-person correlated outcomes will be handled using generalized estimating equations (GEE; Zeger, Liang, & Albert, 1988). Measures assessed once will be analyzed using logistic regression. The magnitude of effects will be expressed using odds ratios with 95% CI. Intent-to-treat analyses will be adjusted for covariates used for stratification (Pocock et al., 2002). Two-sided tests with p-values <.05 will be considered significant.

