Primary outcome analyses. We will fit a longitudinal logistic regression model $\text{logit}(Y_{ij}) = \beta_0 + \beta_1 tx + \beta_{2-6}x_{2-6} + \epsilon_{ij}$, where Y_{ij} is the presence of a detectable viral load for the i th person at the j th timepoint (8 visits over two years of treatment), β_1 is the covariate of interest representing the expected decrease in log odds of a detectable viral load as a function of assignment to the treatment group, and β_{2-6} are the coefficients for the 5 randomization covariates. Additional models with time and time by treatment interactions will be fit secondarily to assess time trends in treatment effect.

Secondary outcome analyses. We will fit analogous longitudinal logistic regression models for HRMS-verified ART adherence, self-reported adherence, prescription maintenance, and attendance at HIV medical care visits. We will assess post-treatment effects by fitting analogous models for each outcome, but using only data from the two post-treatment visits.

Moderator analyses. For the primary outcome, we will fit models with interactions between treatment and each of the 5 randomization covariates (drug dependence, alcohol dependence, TOFHLA total score, delay discounting, and Beck Depression score) to assess whether treatment effect varies as a function of the putative moderator. For example, for CIDI drug dependence, we would fit the model $\text{logit}(Y_{ij}) = \beta_0 + \beta_1 tx + \beta_{2-6}x_{2-6} + \beta_7 tx * \text{drug dependence} + \epsilon_{ij}$, where β_1 would represent the treatment effect (expressed as a difference in log odds of a detectable viral load between treatment and control groups) among individuals without drug dependence, and β_7 would represent the difference in treatment effect between individuals with and without drug dependence. All moderator analyses will be considered exploratory and will not be corrected for multiple comparisons. These variables will be examined as potential moderators because drug use (Mimiaga et al., 2013), health literacy (Kalichman et al., 2008),

and depression (Murphy et al. 2013) has each been associated with poor adherence to antiretroviral medications. Impulsivity will be assessed as a potential moderator because high levels of impulsivity have been associated with poor health decision making and adverse health behaviors (Axon et al., 2009; Bickel et al. 2014; Bradford et al., 2010).

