The primary outcome measure of undetectable viral loads will be analyzed with a longitudinal logistic regression model using GEE (Diggle & Diggle, 2002). We used Liu and Liang (1997) to determine the total N required to detect a difference between groups with 80% power. The adjacent figure shows the total number of participants (N) required to detect a difference of 15% between the Usual Care Control and the Incentive Group at the eight 3-month assessments during the intervention evaluation period. The figure shows different percentages for the Usual Care Control group because that value affects the sample size required. 15% is smaller than the effects produced in all prior studies of voucher reinforcement of cocaine or opiate abstinence or medication adherence and smaller than all effects produced by the Therapeutic Workplace and smaller than the incentive effects in promoting drug abstinence, medication adherence and other health behaviors as shown in three different meta-analyses (Petry et al., 2012; Prendergast et al. 2006; Lussier et al., 2006). The horizontal red lines show the number of participants planned based on the number of participants enrolled and randomized to the two groups without (top dashed line) and after adjusting for the anticipated rates of missing data (20% missing, bottom solid red line). Based on this analysis, we need to enroll and randomize 200 participants (horizontal dashed line) to ensure that we have sufficient sample sizes after adjusting for the rates of missing data. After adjusting for missing data (20% missing), this would yield a sample size of 160 participants (200 participants x 0.80 collected samples = 160 participants). The adjusted sample size of 160 participants (solid red line) is a little more than the maximum number of participants that would be required.

c. Early stopping rules.

The protocol can be stopped based on recommendations of the Scientific Advisory Committee overseeing this study. We will ask the Scientific Advisory Committee to recommend that the trial be stopped if a review of the adverse events suggests to any of the investigators that the number of related and unexpected adverse events is unacceptably high. The Scientific Advisory Committee will be allowed to request statistical analyses to compare the groups on the rates of different adverse events or to have the adverse event data summarized in other ways that they deem appropriate.

Risks

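### Clinic of HIV care is in neither the urn nor the outcome models; adding it as a covariate is a cheap precision gain if the clinics differ

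*Combined protocol and SAP*

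**What the plan says.** **Allocation.** Section 4a, Experimental Design, describes individual randomisation by an urn that "will be used to balance groups on five baseline characteristics that may influence outcome". The factors are a drug-positive urine, drinking to intoxication, health literacy, delay discounting and depression. Clinic is not among them.

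**Analysis.** Section 7b limits covariate adjustment to the stratification factors. In the primary model, the terms beyond treatment "are the coefficients for the 5 randomization covariates". The secondary models are described as analogous.

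**Comparator.** The abstract states: "Usual Care Control participants will only receive the standard HIV medical care offered in their clinic". The Usual Care Control Group paragraph in 4a says the same.

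**Which clinics.** The abstract has "Participants (N = 200) from two medical clinics that serve adults living with HIV in Baltimore will be randomly assigned". Section 4a, Standard HIV Medical Care, is looser: "Participants will typically receive their HIV medical care at the Comprehensive Care Practice or the Chase Brexton Health Services clinic". Recruitment also draws on other programs and word of mouth (4a, Study Participants). Section 5 admits people who are not in HIV care, and 4a says they are referred to a clinic.

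**The concern.** The urn factors were chosen because they may influence outcome. The source of HIV care plausibly meets that test too, and the plan gives no reason for leaving it out.

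Clinic may matter in two ways. Clinics can differ in case mix and in the share of patients they keep suppressed. Clinic can also affect how the outcome is obtained: viral loads come from medical records when possible (Risks, item a) and from the participant's clinic under the COVID-19 procedures in 4a, while 7b counts missing values as detectable. A clinic whose results are harder to get would show more failures even if true suppression were equal.

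If clinics do differ, leaving the term out keeps between-clinic variation in the error of the primary comparison and leaves chance clinic imbalance in the estimate. Section 7b, Power Analysis, describes the adjusted sample of 160 as only slightly above the largest number needed, so there is little margin.

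**Working it through.** **Inputs from the documents**
- Significance: "Two-sided tests with p-values <.05 will be considered significant" (7b).
- Power: the calculation was done "to determine the total N required to detect a difference between groups with 80% power" (Power Analysis).
- Effect: the N "required to detect a difference of 15% between the Usual Care Control and the Incentive Group", over eight assessments.
- 200 randomised, 20% missing, 160 after adjustment.

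**Inputs assumed, because the text does not give them**
- Equal allocation to the two arms.
- Worst-case rates of 42.5% versus 57.5%. The control rates used are in a figure that is not shown.
- Exchangeable within-person correlation ρ.
- Share s of participants at one of two clinics, taken as 0.5.
- Between-clinic gap d in percent suppressed, 5 to 20 points.

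**1. The plan's own figure.** 200 × 0.80 = 160, as stated. For a single assessment, two-sided 0.05 and 80% power:

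n per arm = [1.96·√(2 × 0.5 × 0.5) + 0.842·√(0.425 × 0.575 + 0.575 × 0.425)]² / 0.15² = 174 after rounding up, so 348 in total.

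Eight repeated assessments multiply this by (1 + 7ρ)/8. With ρ = 0.36 the factor is 0.44 and the total is 154; with ρ = 0.40 it is 166. A requirement just under 160 therefore fits ρ of about 0.36 to 0.38. This is an inference and cannot be confirmed from the text. ρ = 0.36 is used below.

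**2. Share of variance due to clinic.** The variance of a person's eight-visit mean is about 0.25 × (1 + 7 × 0.36)/8 = 0.11. Clinic contributes s(1 − s)d² = 0.25d². The ratio is R² = 0.25d²/0.11.

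**3. Power if clinic is added, starting from 80%.** Power = Φ(2.80/√(1 − R²) − 1.96). Equivalently, 160 participants analysed without clinic are worth 160(1 − R²) analysed with it.

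**4. Chance imbalance.** With 200 randomised, the SD of the between-arm difference in clinic share is √(4 × 0.5 × 0.5/200) = 7.1 points, with 95% limits of ±13.9 points. Multiplying ±13.9 by d gives the shift in the treatment difference.

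| Gap d | R² | Power with clinic added | 160 without clinic equals | Shift, 95% limits |
|---|---|---|---|---|
| 5 points | 0.006 | 80.2% | 159.1 | ±0.7 points |
| 10 points | 0.023 | 80.9% | 156.4 | ±1.4 points |
| 15 points | 0.051 | 82.0% | 151.8 | ±2.1 points |
| 20 points | 0.091 | 83.6% | 145.5 | ±2.8 points |

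**5. Sensitivity.** With ρ = 0.5 and a 50:50 split, power becomes 80.7% (10 points) and 82.8% (20 points). With ρ = 0.36 and a 70:30 split, it becomes about 80.8% and 83.0%.

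**6. Simulation.** Logistic GEE with robust person-level variance, 160 people, eight visits, 1,500 replicates per setting, allocation not balanced on clinic:
- Power without versus with a clinic term: 81.8% versus 82.1% (clinics about 10 points apart) and 77.5% versus 81.3% (about 20 points apart). Monte Carlo error is about 1 point, so the first difference is within noise.
- Type I error with clinic omitted: 5.7% and 4.7%, both close to nominal.
- Clinics about 20 points apart, allocation balanced on clinic: 79.1% without the model term and 81.3% with it. The gain comes mainly from the covariate, not from the urn.

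**The case against.** The plan is coherent as it stands. It names its prognostic factors, balances on them and adjusts for them, and both arms receive their own clinic's care. Under individual randomisation, chance clinic imbalance is already reflected in the standard error. That stands. A reader might infer that the omission biases the comparison or invalidates the test; neither the design nor the simulation supports this.

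A reader might also infer that power is certainly being lost, perhaps a good deal of it. A 25-point gap with ρ = 0.3 and a 50:50 split gives R² = 0.161, power of 86%, and a gain worth 200 × 0.161/0.839 = 38 participants. The documents give no clinic gap at all, and 25 points exceeds the trial's own 15-point target. That corner should not be taken as the expected gain.

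The five covariates may absorb part of any clinic difference that comes from case mix, so the figures above are upper limits for their assumptions. This also stands. They are less likely to absorb differences in how results are obtained.

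Clinic is not a clean two-level factor, since some participants attend elsewhere or have no clinic at intake. The records release signed at screening cannot identify a clinic for someone who has none. This limits how the variable must be defined but does not prevent its use.

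Finally, a covariate added late in an open-label trial can look data-driven. That is fair, and it makes the timing of the change part of the fix. Adding clinic also alters the meaning of the odds ratio slightly, but that odds ratio is already conditional on five covariates.

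**Conclusion.** The omission is plain in the text: clinic of care at intake is in neither the urn nor the primary or analogous secondary models, although clinic defines the comparator. It affects precision only. The plausible gain from adjusting is about 1 power point if clinics are 10 points apart and about 4 if they are 20 apart. That rests on the assumed 50:50 split and ρ of about 0.36, and comes before any overlap with the existing covariates. If clinics do not differ, there is no gain. The possible chance shift of 1.4 to 2.8 points compares with a standard error of about 15/2.80 = 5.4 points, so it is a minor part of the total uncertainty. Nothing here shows the sample size to be wrong. This is a cheap improvement.

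**What to change.** In section 7b, add clinic of HIV care, as recorded before randomisation, as a fixed covariate in the primary model and the analogous secondary models. Use the two named clinics, other, and none as levels, and state in advance the rule for pooling sparse levels. A participant with no clinic at intake is coded by that status, not by a clinic joined after randomisation. Fix the wording before any between-arm outcome comparison, and report the model without clinic alongside it.

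Make clinic a sixth urn factor only if anyone remains to be randomised. The COVID-19 paragraph refers to remaining assessments, which suggests that enrolment may be over. If so, the covariate alone recovers nearly all of the gain.

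The cost is a sentence or two in 7b and two or three model terms. For participants already in care, the clinic should be known from the screening release. For the others, the only requirement is to record that they had none.
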